### 7.1.3 Indication for systemic therapy

Symptomatic mild chronic GvHD may often be managed with local therapies alone (eg, topical corticosteroids for the skin involvement).

In contrast, in patients with moderate or severe chronic GvHD (eg chronic GvHD that involves 3 or more organs or with a score of 2 or greater in any single organ), systemic immunosuppressive therapy should be considered.

However, in some organ sites (mouth, eyes, genital tract), aggressive local therapy alone may be reasonable, as response to systemic therapy may be suboptimal or may not warrant the risk of treatment.

## 7.2 Pre-treatment evaluations (1 week before ATO treatment)

In addition to chronic GvHD assessment detailed above, the following evaluations must be performed within one week prior to the first ATO cycle:

- Patients' sociodemographics including data on age, gender, and contraception
- Recipient, donor and transplant characteristics
- DLI modality (if relevant)
- Evaluation of GvHD using the chronic GvHD Activity Assessment-Clinician Form A (see below and Appendix 8)
- Patient self-reported outcome using the chronic GvHD activity assessment-patient self-report (Form B) (see Appendix 9)
- History of GvHD prophylaxis : documentation of any associated treatments and topical therapy since graft for acute GvHD or progressive form of cGvHD treated by corticotherapy < 1 mg/kg/day, whenever possible given collected clinical history
- Concomitant diseases
- Physical examination, including vital signs, weight and size (see Appendix 4 to Appendix 5)
- Documentation of daily steroid dose
- Documentation of any associated treatments and topical therapy for chronic GvHD (including glucocorticoid creams, topical tacrolimus, oral beclomethasone or budesonide, topical azathioprine and ophthalmic glucocorticoids...)
- Hematology: complete blood count (CBC) with differential counts (leucocytes, neutrophils, lymphocytes, monocytes, eosinophils counts, hemoglobin, platelets)
- Serum Chemistries: creatinine, uric acid, total bilirubin, alkaline phosphatases,

LDH, total protein, albumin, SGOT (Aspartate amino-transferase, ASAT), SGPT (Alanine amino-transferase, ALAT), calcium, glycaemia

- Infectious disease surveillance: cytomegalovirus (CMV), Epstein Barr virus (EBV) and other infectious diseases (Hepatitis [hep] B surface Antigen (Ag), Hep B surface antibody if relevant)
- Immunology: quantitative immunoglobulin measurement; lymphocyte subset analysis of B cells, T cells, and auto-antibodies
- Tumor evaluation
- Quality of life questionnaire (LSS and FACT-BMT) (see Appendix 10 to Appendix 11)
- The patient must undergo an electrocardiogram (EKT) before ATO treatment with QTc measurement
- In addition, serum levels of electrolytes (potassium, magnesium) will be measured
- If appropriate, a serum pregnancy test will be performed at the study start before any administration of the study drug
- Other tests including pulmonary function (FEV1) and imagery (chest-X ray) tests will be carried out
- A cutaneous biopsy if relevant and a coagulation test with measurement of PT and APTT will be performed

### **7.3 Inclusion and treatment plan**

#### **7.3.1 Inclusion**

If a patient fulfills the inclusion criteria of the protocol and has signed the informed consent, he will be eligible for inclusion in the study. For inclusion purposes, a specific “Registration form” will be used, and the patient will be given a unique identification number, according to standard procedures.

The consent form must be documented by obtaining the dated signature both of the patient and of the person involved in the study, conducting the consent discussion on the consent form (see Appendix 14). The patient should have an oral and written language able to perfectly understand the language of the informed consent form. The

investigator site should write in the patient file who submitted the informed consent and the date of the submission and signatures.

The consent form should be signed before any procedure related to the protocol.

A copy of the informed consent and consent form should be given to the patient before participation, the original should be kept by the investigator site.

The initial informed consent and any amendment should be reviewed and approved by the Protection of Persons Committee (CPP) before submission and signature.

The patient and his/her legally representative should be informed in a timely manner if new information becomes available that may be relevant to the patient's willingness to continue participation in the study. This should be documented in the patient file.

Registration of patients included in the study will be performed in the PROMISE database of the European society for Blood and Marrow Transplantation (EBMT) and in the specific electronic CRF of the study.

When connecting to the electronic CRF patient and inputting criteria for inclusion/exclusion, a number will be automatically assigned to the patient. This number will serve as reference for any exchange with the Sponsor.

### **7.3.2 Treatment plan**

#### ***7.3.2.1 Arsenic trioxide therapy***

As soon as the diagnosis of chronic GvHD requiring systemic immunosuppressive therapy is confirmed, patients will receive in addition to cyclosporine A (if relevant) and corticosteroids 1 mg/kg/day, ATO 0,15 mg/kg/day over a 4 weeks period (one cycle).

The treatment plan is indicative, but it is important to respect the number of 11 perfusions per cycle. In the case of a temporary discontinuation of ATO therapy for medical or other reasons, the canceled infusions will be scheduled as soon as possible.

- Week 1: day 1 to 5
- Week 2: 3 times per week (example: day 8, 10 and 12)
- Week 3: 2 times per week (example: day 15 and 17)
- Week 4: 1 time per week (example: day 24)

ATO should be administered within 10 days of starting prednisone 1mg/kg/day. Follow-up dates for response assessment and laboratory tests relate to the date of ATO infusion. Patients in partial response after the 1st cycle of ATO will be eligible to receive a second cycle of ATO as consolidation therapy. A delay of 8 weeks to a maximum of 11 weeks (from the first infusion of ATO) will be observed between the two cycles of ATO therapy.

Response definition is as follows:

- Complete remission (CR) is defined as complete disappearance of any sign of chronic GvHD
- Partial remission (PR) is defined as improvement of 1 or more point on a 4 to 7-point scale or an improvement of 2 or more points on a 10 to 12-points scale in at least 1 organ or site without progression in any other organ or site. For patients with BOS, an absolute improvement in %FEV1 of 10% predicted or more (eg, 50% to 60%) is considered a PR as long as the initial % FEV1 is < 70%. Normalization ( $\geq 80\%$ ) is considered a CR.
- Progressive disease (PD) is defined as at least one organ system has worsened by at least one stage without improvement of any other organ systems from baseline:
  - For skin, eye, esophagus, and upper and lower gastro-intestinal (GI) tract, a worsening of 1 point or more on the 0 to 3 scale is considered progression, except a change from 0 to 1, which is considered trivial progression since it often reflects mild, nonspecific, intermittent, self-limited symptoms and signs that do not warrant a change of therapy.
  - For joint/fascia, a worsening of 1 point or more on the 0 to 3 scale is considered progression, even if from 0 to 1, because a change to score 1 was considered meaningful progression that would prompt a change in therapy. For joints assessed by the photographic range of motion, a worsening of 1 or more points for the 7-point scales and 1 or more points for the 4-point scale is considered progression.
  - For mouth, a worsening of 2 or more points on the 1-point scale indicates

progression.

- Worsening of liver GvHD is defined by an increase of 2 or more times the upper limit of normal for the assay for alanine transaminase, alkaline phosphatase, or total bilirubin.
- For patients with lung involvement, absolute worsening of FEV1 by 10% predicted or more (eg, 50% to 40%) is considered progression, as long as the final %FEV1 is < 65% (because initial %FEV1 must be < 75% to establish the diagnosis of lung involvement). If PFTs are not available, then worsening of the clinical lung score based on symptoms by 1 or more points should be scored as progression, except from score 0 to 1, which is considered trivial progression because of its lack of specificity for lung chronic GvHD.
- Mixed response is defined as CR or PR in at least one organ accompanied by progression in another organ
- Unchanged: outcome that do not meet criteria for CR, PR, PF or mixed response are considered unchanged

Response determination for chronic GvHD is indicated in the table below:

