## 4. Patients selection

### 4.1 Inclusion criteria

Patient will be eligible for inclusion in this study if the patient met all the following criteria:

- Adult patients ( $\geq 18$  years) who have received a first allogeneic stem cell transplantation for a hematological disease (any source of hematopoietic stem cells is authorized; any category of conditioning regimen prior to allo-SCT is authorized; any type of stem cell donors is authorized)
- Confirmed diagnosis of first episode of chronic GvHD requiring systemic immunosuppressive therapy (any prior GvHD prophylaxis previously used is accepted). Chronic GvHD diagnosis is defined according to the National Institutes of Health (NIH) Working Group Consensus. Chronic GvHD diagnosis will be based on the evaluation of the severity of the different clinical manifestations including:
  - a/ Performance status evaluation
  - b/ Cutaneous evaluation measured by the percentage of extension or the presence of sclerotic features. If relevant, confirmation with a biopsy should be performed whenever possible
  - c/ Oral symptoms
  - d/ Ocular symptoms
  - e/ Gastro-intestinal symptoms
  - f/ Evaluation of liver involvement (total bilirubin, transaminases and alkaline phosphatases)
  - g/ Pulmonary function evaluation
  - h/ Evaluation of the musculoskeletal manifestations, especially the amplitude of the relevant articulations
  - i/ Genital tract symptoms
- Signed informed consent (see Appendix 14)
- Absence of contra-indications to the use of ATO

- Subjects affiliated with an appropriate social security system
- Men must use a medically acceptable method of contraception throughout the treatment period and for at least 4 months and 10 days following the last treatment administration
- Women who are of childbearing potential must have a negative serum pregnancy test and agree to use a medically acceptable method of contraception throughout the study and for 3 months following the end of the study
- Patient not participating or not having participated in a clinical study in the 30 days prior to his/her inclusion in the study

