### **7.1.2 Definition of mild, moderate and severe chronic GvHD**

Eight organs or sites (skin, mouth, eyes, gastrointestinal tract, liver, lungs, joint and fascia, and genital tract) are considered for calculating global score. Elements included in the proposed global scoring include both the number of organs or sites involved and the severity score within each affected organ. Performance status scoring is not incorporated into the global scoring system. Organ scoring is performed according to the NIH Working Group consensus (Jagasia et al., 2015) (see Appendix 2).

For skin, the composite score is split into 2 scores to document the extent of skin involvement (BSA) and the specific skin features, separately (see Appendix 6). The higher of the 2 scores is to be used for computation of global severity.

Eyes, are better assessed by a specialist, however, it is not mandatory.

For lung, pulmonary function tests to assess the first forced expiratory volume (FEV1) are mandatory in this protocol. The composite score is split in 2 score, a symptom score and a FEV1 score based. In case of discrepancy between both score, the FEV1 score is used for the final lung scoring.

For genital tract, scoring is based on severity of the signs instead of symptoms, both in man and woman, according to the figure provided in Appendix 3. Genital tract scoring must be performed by a specialist or a trained practitioner in chronic GvHD grading. Female or male genital GvHD is not scored if a practitioner is unable to examine the patient.

For joint and fascia, the photographic-range and motion (P-ROM) score is an exploratory measure and is not included in the calculation of global severity.

Abnormality present but explained entirely by non-chronic GvHD documented cause must be specified and the organ will be excluded from calculation of the global severity.

Computation of the chronic GvHD global severity, as mild, moderate or severe is indicated in the table below:

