**Table 3. NIH global severity of chronic GvHD**

Mild	1 or 2 Organs involved with no more than score 1 plus Lung score 0
Moderate	3 or More organs involved with no more than score 1 OR At least 1 organ (not lung) with a score of 2 OR Lung score 1
Severe	At least 1 organ with a score of 3 OR Lung score of 2 or 3

Key points:

- In skin: higher of the 2 scores to be used for calculating global severity.
- In lung: FEV1 is used instead of clinical score for calculating global severity.
- If the entire abnormality in an organ is noted to be unequivocally explained by a non-GvHD documented cause, that organ is not included for calculation of the global severity. If the abnormality in an organ is attributed to multifactorial causes (GvHD plus other causes) the scored organ will be used for calculation of the global severity regardless of the contributing causes (no downgrading of organ severity score).

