- For joint and fascia, scoring from 0 to 3 is based on symptoms. The P-ROM score is an exploratory measure that could be very useful in that exploration.
- For mouth, scoring from 0 to 12 is based on symptoms.
- For gastrointestinal tract, scoring from 0 to 3 is performed for the upper and lower gastrointestinal tract and esophagus. In addition patient weight must be recorded.
- For liver, total serum bilirubin, alkaline phosphatase and alanine aminotransferase must be recorded.
- Genital tract requires a specialist exam and measure of genital response are considered exploratory. Therefore, genital tract is not included in evaluation of chronic GvHD response.

Abnormality present but explained entirely by non-chronic GvHD documented cause must be specified and the organ will not be considered as involved for evaluation of chronic GvHD response.

In addition, physician should provide a subjective assessment of current overall chronic GvHD severity on a 4-points scale (no chronic GvHD, mild, moderate or severe) without knowledge of the calculated NIH global severity score. They should also provide an assessment of current overall chronic GvHD severity on a 11-point numerical scale (0 indicates no GvHD manifestation; 10 indicates most severe chronic GvHD symptoms possible). Clinicians should also provide their evaluations of chronic GvHD changes since the last assessment scored on a 7-point scale (very much better, moderately better, a little better, about the same, a little worse, moderately worse, very much worse). These semi-quantitative assessments may detect qualitative improvements that are clinically meaningful but not well captured using other measures.

➤ **Patient reported outcome**

Patient reported outcome included chronic GvHD-specific core measure with the chronic GvHD activity assessment-patient self-report (Lee Symptom Scale: LSS - Form B) and chronic GvHD non-specific ancillary measure with the FACT-BMT. Patients reported outcome are exploratory and will not be used for decision making response evaluation.

- Organ sites considered in the chronic GvHD activity assessment-patient self-report included skin and joint, mouth, genital tract and eyes. In addition, similarly to clinician assessed chronic GvHD, at each assessment, patients should score their perceptions of overall chronic GvHD severity, overall severity of symptoms, and change in symptom severity compared with the last assessment, using the same response options used by clinicians.

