17. APPENDICES

17.1 RESPONSE CALCULATION ALGORITHM

Etude GMED_16_001 : Evaluation des réponses complètes et partielles – 19/10/2020

Les réponses sont définies comme (règles de calcul basées sur le protocole et l'article Lee et al)

- Complete response at a visit: Lorsque tous les scores de « cGVHD activity assessment form A » des organes suivants sont à 0 ou que la variable "abnormalities present but explained entirely by non-GVHD documented cause » soit égale à Oui.

Détails :

Si une valeur est manquante pour un des organes atteints lors de la visite V1, la réponse ne peut pas être considérée comme complète. le fait que la valeur est manquante sera documentée.

Si une valeur à la visite d'intérêt est manquante sur un organe non atteint lors de la visite V1, la réponse complète peut être établie, car les réponses complètes ou partielles ne sont établies que sur les organes atteints à V1.

Si « abnormalities present but explained entirely by non-GVHD documented cause » = Oui pour un organe à la visite considérée, le score de cet organe n'est pas corrigé et cet organe n'est pas considéré pour l'évaluation de la réponse complète. cela ne créera pas de valeur manquante pour cet organe et n'empêchera pas la réponse d'être considérée comme complète si les informations sur les autres organes sont disponibles.

- BSA=0 ET skin features=0

M6_GVHD_A_S (préfixe M6 ou C1W6, W14, M9 et M12 selon la visite considérée)

M6_GVHD_A_S_F_S

M6_GVHD_A_S_ABN

- Eyes=0

M6_GVHD_A_E

M6_GVHD_A_E_ABN

- Gastrointestinal=0 (pour chacun des 3 scores : Gastro-oesophageal, Gastro-upper, Gastro-lower)

M6_GVHD_A_GASTRO1

M6_GVHD_A_GASTRO2

M6_GVHD_A_GASTRO3

M6_GVHD_GAST_ABN

- Mouth=0 (considérer la somme des 3 scores : Erythema, Lichenoid, Ulcers)

M6_GVHD_A_MOUTH1
 M6_GVHD_A_MOUTH2
 M6_GVHD_A_MOUTH3
 M6_GVHD_MTH_ABN

Joint and fascia =0

M6_GVHD_A_J
 M6_GVHD_A_J_ABN

Liver : les 3 valeurs (Bilirubine, ALAT et PAL) sont en dessous des ULN (Unité limite supérieure) si le score hépatique était >0 à V1 (table 1 et annexe du protocole)

.<M6_GVHD_A_L_SGPT_V<=M6_GVHD_A_L_SGPT_U_V
 .<M6_GVHD_A_L_ALK_V<=M6_GVHD_A_L_ALK_U_V
 M6_GVHD_LIV_ABN

Le score à V1 est calculé comme :

Score = 0 : Bilirubine normale WITH ALAT AND PAL < 3 UNL

(.<V1_GVHD_A_L_BILI_V<=V1_GVHD_A_L_BILI_U_V et
 .<V1_GVHD_A_L_SGPT_V<3* V1_GVHD_A_L_SGPT_U_V et
 .<V1_GVHD_A_L_ALK_V<3* V1_GVHD_A_L_ALK_U_V)

Score = 1 : Bilirubine normale WITH 3 UNL<=ALAT < 5 UNL AND 3 UNL <=PAL<5 UNL

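### CR is defined as loss of every sign of chronic GvHD, but the computed response ignores the genital tract and has no rule for a patient with no evaluated organ involved at baseline

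*Protocol*

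**What the plan says.** **Diagnosis and severity.** Protocol 4.1 lists "Genital tract symptoms" among the manifestations on which diagnosis rests. Protocol 7.1.2 says: "Eight organs or sites (skin, mouth, eyes, gastrointestinal tract, liver, lungs, joint and fascia, and genital tract) are considered for calculating global score". Under Table 3, one non-lung organ with score 2 is moderate disease, and the severe category is "At least 1 organ with a score of 3 OR Lung score of 2 or 3". Protocol 4.2 excludes single-site moderate disease only where systemic therapy is not needed. Protocol 7.1.3 adds that "in some organ sites (mouth, eyes, genital tract), aggressive local therapy alone may be reasonable".

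**Response.** Protocol 7.3.2.1, Protocol 9.3 and SAP 8.2.1 all carry the same sentence: "Complete remission (CR) is defined as complete disappearance of any sign of chronic GvHD". Protocol 9.2 explains that genital assessment needs a specialist and is exploratory, and concludes: "Therefore, genital tract is not included in evaluation of chronic GvHD response". Protocol Table 4, its copy in SAP 8.2.1, the by-organ table in SAP 11.4.2.1 and Form A as reproduced in Protocol Appendix 8 have no genital item.

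**Computation.** SAP 17.1 declares CR when all Form A scores "des organes suivants sont à 0" (for the organs listed there), or when the abnormality is fully attributed to a cause other than GvHD. No listed variable is genital. The same appendix says that "les réponses complètes ou partielles ne sont établies que sur les organes atteints à V1", meaning that CR and PR rest only on organs involved at V1. It sets organ-level CR and PR to missing for organs not involved at V1.

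**Use.** The main analysis (SAP 11.4.1.1) takes CR or PR as judged by the PI, and also reports CR and PR separately with exact intervals. The computed response enters sensitivity analyses b and d (SAP 11.4.1.2).

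**The concern.** The site that helps to qualify a patient and set severity is outside the response assessment, yet the CR sentence makes no exception for it. Two questions follow.

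1. A patient whose evaluated organs clear while genital signs remain is CR by SAP 17.1 but not CR by the written definition. The PI, whose judgement is the main analysis, has one rule in 7.3.2.1 and another in 9.2. The PI and computed responses can then differ for a reason unrelated to data quality, and the CR and PR rates depend on which scope was used.
2. A patient with no listed organ involved at V1, such as one with genital disease alone, has nothing on which response can be computed. If the algorithm nevertheless returns CR, the computed analyses contain a responder who has not improved.

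The CR/PR label after the first cycle also feeds second-cycle eligibility (Protocol 7.3.2.1) and the prednisone path at week 6 (Protocol 6.2), so sites need a single meaning.

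**Working it through.** **Step 1: the plan's own design.** Inputs from Protocol 10.7: p0 = 0.60, p1 = 0.85, n = 21, success at 17 or more, target alpha 0.05, beta 0.20, dropout about 10%.

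- Type I error = P(X ≥ 17 | n = 21, p = 0.60) = 0.0370.
- Power = P(X ≥ 17 | n = 21, p = 0.85) = 0.8025.
- 21 is the smallest n that meets both limits, and 21/(1 − 0.10) = 23.3, rounded up to 24.

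The stated design reproduces.

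**Step 2: SAP 17.1 applied to example patients.** Two readings were used. The lead rule is that all listed scores are 0. The V1 rule is that only listed organs involved at V1 count.

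| V1 to M6 | Lead rule | V1 rule | Written CR sentence |
|---|---|---|---|
| Skin 2→0, genital 2→2 | CR | CR | not CR |
| Skin 2→0, genital 1→3 | CR | CR | not CR |
| Genital only 3→3 | CR | undefined | not CR |
| Genital only 3→3, new eye score 1 | not CR | undefined | not CR |

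Rows 1 and 2 do not depend on the reading: computed CR coexists with persisting or worse genital disease. In row 1 the skin improvement still meets PR, so the conflict moves one patient between CR and PR and leaves CR+PR unchanged. In row 2 the effect depends on whether the no-progression condition of PR covers the genital tract. Protocol 7.1.2 counts it as a site, but 9.2 and Table 4 give no genital progression criterion.

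**Step 3: size for a patient with no listed organ involved at V1 (lead rule only).** The documents give no count, so k below is an assumption. Each such patient adds 1/21 = 4.8 percentage points to computed CR+PR. One could turn 16/21 (76.2%) into 17/21 (81.0%). If k of 21 are responders by construction, the type I error of the 17/21 rule is P(X ≥ 17 − k | n = 21 − k, p = 0.60):

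| k | Type I error |
|---|---|
| 0 | 0.037 |
| 1 | 0.051 |
| 2 | 0.070 |
| 3 | 0.094 |

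This applies the protocol's rule to the computed response with 21 patients. It does not describe the main analysis.

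**The case against.** The strongest reply is that the exclusion in Protocol 9.2 is deliberate and reasoned, and that Table 4, Form A, the by-organ table and SAP 17.1 follow it consistently; only the general CR sentence was left unqualified. That stands, and it fixes the nature of the defect: the CR wording and the operational rules were not aligned.

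Three stronger readings are tempting but not supported.

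- *A genital-only patient is automatically CR at every visit.* This follows from the lead rule in SAP 17.1 only while no listed organ becomes abnormal. The V1-involvement sentences can be read as leaving the result undefined, and Table 4 asks for previous involvement in its organ rows. The lung line, taken literally, requires a V1 FEV1 below 70, which normal lungs cannot meet. It does not settle the matter, because it would deny CR to every patient with normal baseline lungs.
- *The primary result is inflated.* The main analysis is PI-judged CR+PR. Stable residual genital disease does not alter that count, and the computed response serves only analyses b and d.
- *The PI has no means of recording genital disease.* The Global row of Table 4, based on the clinician's overall severity score, is not limited to organs and could capture it. SAP 17.1 does not use that row.

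It is also fair that genital-only patients are probably rare: 7.1.3 suggests local therapy may suffice, and 4.2 excludes single-site moderate disease that does not need systemic therapy. Severe disease, or single-site disease that does need systemic therapy, is not excluded.

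**Conclusion.** The point holds in a limited form. The unqualified CR sentence conflicts with the exclusion in Protocol 9.2, and SAP 17.1 can compute CR with genital disease present. The consequence is for the separate CR and PR rates and for agreement between PI and computed responses. CR+PR is unchanged when the residual genital disease is stable.

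Separately, SAP 17.1 lacks a rule for a patient with no listed organ involved at V1. On the literal lead rule each such patient is worth 4.8 points of computed CR+PR, and a single one takes the 17/21 rule from 0.037 to 0.051, just above the 0.05 target. This rests on that reading, on 21 analysed patients and on at least one such patient being enrolled, none of which the documents establish. How many percentage points of the CR rate are at stake cannot be stated, because no frequency of genital involvement is given.

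**What to change.** 1. **SAP 17.1**, add: *A computed global CR or PR requires at least one Table 4 organ involved (score ≥ 1, not explained by a non-GvHD cause) at V1; otherwise the patient is counted as a non-responder in the computed analyses and listed.*
2. **Protocol 7.3.2.1 and 9.3, and SAP 8.2.1**: reconcile the CR sentence with Protocol 9.2 and SAP 17.1, so that the PI and the algorithm use one stated scope of organs.
3. **SAP listings**: list computed CRs in patients with genital involvement recorded at V1, so that a reader can see how many there are. The organ tables in SAP 11.2.3 do not show this at present.

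Because the CR/PR label also enters Protocol 7.3.2.1 (second cycle) and 6.2 (prednisone), the sponsor must reconcile those passages with the chosen scope. No clinical rule is proposed here. Capping response at PR for residual genital disease is not recommended: it would undo the reasoned exclusion in 9.2 and depend on an examination that 7.1.2 reserves for a specialist or trained practitioner. No change to eligibility is proposed either.

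The cost is a few sentences and one listing. The downside is that a rare patient moves from computed responder to non-responder, including one whose genital disease did improve.
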